1. SAMPLE SIZE AND JUSTIFICATION

A pilot randomized controlled trial with 70 OCS (n=35 for intervention arm; n=35 for control arm) is the most efficient design to accomplish the aims of this pilot study.⁶¹⁻⁶³ For this study, the minimum sample size is calculated using G*Power. Specifying alpha level to be 0.05 (one-sided), expected power to be 0.80, and an expected effect size of 0.50 for the primary outcome (physical function measured by SPPB), the sample size required is 27 per group. Effect size estimates are based on recommendations for clinically meaningful differences for the SPPB^{64,65} and previous pilot randomized controlled trials utilizing the SPBB reporting effect sizes of similar magnitude.^{66,67} Similar designed pilot randomized controlled trials^{38,68-70} used comparable sample sizes to demonstrate acceptability and feasibility.

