2. DATA ANALYSIS PLAN

Aim 1: The feasibility of implementing a 12-week online diet and resistance training intervention with OCS will be determined by the study accrual rate, retention rate, and adherence rate. The study accrual rate will be calculated by dividing the number of potential participants that passed screening by the total number of participants started in the study after appropriate informed consent procedures. The recruitment goal is set at 70 participants recruited over a 9-month period. Retention rate will be calculated by dividing the total number of participants initiated by total number of participants in the study at baseline and 12 weeks (end-of-study). Retention goal for this trial is 80%. If 80% (56/70) of participants are retained at end-of-study, the retention goal for this trial will be achieved. Previous studies by the study team had similar recruitment and retention rates of older participants.⁷¹⁻⁷³ We are confident in our ability to recruit and retain the study participants necessary to conduct the proposed study. Participants will be determined to be adherent if they attend ≥80% of the intervention sessions (in-person meetings with study staff and online intervention sessions).^{71,74,75} Overall adherence and

retention rates and associated 95% confidence intervals will be reported at baseline, end-of-study, and 3-month follow-up.

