Aim 2: The primary outcome of the SPPB will be assessed at three time points: baseline, end-of-study, and 3-month follow-up. Efficacy will be based on 12 weeks. The SPPB score is a continuous variable, collected as the total score ranging from 0-12. Group differences in SPPB scores over the time will be tested using repeated measures ANOVA (SAS PROC MIXED). Using the planned contrasts command, we will investigate the changes in SPPB scores within each group, and between the intervention and control groups at end-of-study. Descriptive statistics and frequency distributions will be used to characterize the sample. To examine the effect of the intervention on the changes in physical function, a linear mixed effect model will be adopted using SAS PROC MIXED procedure. The intervention group (intervention vs. control) and time points (baseline, end-of-study, 3-month follow-up) serve as the categorical predictors, together with the intervention*time interaction term. A significant intervention*time interaction effect would indicate a differential change pattern over the time between the groups. Using post-hoc contrasts, we will compare group differences in all collected variables at each time point. Using planned contrasts command, we will investigate for each group the change from baseline to end-of-study, from end-of-study to 3-month follow-up, and from baseline to 3-month follow-up to capture the change patterns over the phases and Bonferroni correction will be applied. Preliminary effect sizes will be generated to inform future trials. A Shapiro-Wilk test, skewness, kurtosis, and Q-Q plots will be used to assess normality of survivor baseline and end-of-study outcomes. Based on normality tests, change in participant outcome measures from baseline to end-of-study will be assessed using paired t-tests or Wilcoxon's signed rank tests.⁷⁶ Analysis will be carried out using intent-to-treat (all participants) and modified intent-to-treat (adherent participants only). All quantitative analyses will be performed using SAS version 9.4.

REFERENCES References

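### For the continuous secondary efficacy outcomes, the analysis plan states no between-arm estimate of change and no baseline-adjusted between-arm contrast; the test of change it names is within-person.

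*Combined protocol and SAP*

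**What the plan says.** The Study Design section promises a comparison of the experimental and control groups over the 12 weeks on physical function and on the associated health outcomes. The Aim 2 hypothesis, by contrast, is worded as improvement among intervention participants.

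The Aim 2 paragraph of section V.2 (Data Analysis Plan) then sets out these analyses:

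- **Arm-by-time model.** "To examine the effect of the intervention on the changes in physical function, a linear mixed effect model will be adopted", with arm, time and their interaction as terms. The outcome named is physical function; the repeated-measures ANOVA sentence before it also names only the SPPB.
- **Between-arm contrasts for everything.** "Using post-hoc contrasts, we will compare group differences in all collected variables at each time point". No baseline term and no difference in change is mentioned.
- **Contrasts of change for each group.** These are within-arm, and no outcome is named.
- **Test of change.** Depending on normality checks, "change in participant outcome measures from baseline to end-of-study will be assessed using paired t-tests" or Wilcoxon signed-rank tests.
- **Analysis set.** "Analysis will be carried out using intent-to-treat (all participants") and, as a second set, adherent participants only.

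No method for missing data is given. The Study Termination Procedures say that the surveys of participants who decide to stop are deleted.

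**The concern.** A two-arm trial estimates a treatment effect from the contrast between arms. For the secondary efficacy outcomes, the only analysis of change that the plan spells out looks at each person before and after. Repeat testing, season, or the act of volunteering can shift both arms. A paired test in the intervention arm cannot separate such a shift from an effect of the intervention. The stated alternative for non-normal data, the signed-rank test, has the same limit.

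The between-arm contrast at 12 weeks does not have this flaw, but as written it ignores a baseline measurement that the trial collects. In a pilot whose effect sizes are meant to inform later trials, that costs precision where precision is scarce.

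A paired test also needs two values per person. That sits badly with an analysis described as covering all participants.

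**Working it through.** **Inputs from the documents**
- Planned size (V.1): "n=35 for intervention arm; n=35 for control arm".
- Retention goal (V.2): "If 80% (56/70) of participants are retained at end-of-study, the retention goal for this trial will be achieved". That is 56/2 = 28 per arm if losses are even, with 70 − 56 = 14 participants lacking a 12-week value.
- Sample-size inputs (V.1): "Specifying alpha level to be 0.05 (one-sided), expected power to be 0.80, and an expected effect size of 0.50 for the primary outcome", giving "the sample size required is 27 per group".

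**Inputs assumed, because the documents give none:** the baseline to 12-week correlation r (0.3 to 0.8), a true difference of 0.5 SD for a secondary outcome, and a drift common to both arms of 0.2 to 0.4 SD of change.

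**1. The plan's own figure.** With d = 0.50 and one-sided 0.05, the noncentral t distribution gives a paired t-test 81.2% power at n = 27 and 79.8% at n = 26. So 27 reproduces exactly as a before-after calculation. A t-test of two independent arms with the same inputs needs 51 per arm. This figure concerns the SPPB, not the secondary outcomes. It does show that a before-after reading of the plan is not far-fetched.

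**2. What a paired test detects when the intervention does nothing.** Suppose both arms drift equally. The two-sided 0.05 paired test in one arm has noncentrality drift × √n:

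| Common drift (SD of change) | n = 28 | n = 35 |
|---|---|---|
| 0.2 | 18% | 21% |
| 0.3 | 33% | 41% |
| 0.4 | 53% | 63% |

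These are correct rejections of no within-arm change. They become false claims only if read as evidence of efficacy.

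**3. What baseline adjustment gains.** In SD units, the unadjusted 12-week contrast has variance 2/n. Adjusted for baseline it has variance (2/n)(1 − r²). The reduction is r²: 0.5² = 25%, 0.7² = 49%, 0.8² = 64%.

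Power for a true 0.5 SD difference (two-sided 0.05, normal approximation) is Φ(0.5/SE − 1.96). At 28 per arm the unadjusted SE is √(2/28) = 0.267, and 0.5/0.267 = 1.87, so power is Φ(−0.09) = 46%. At r = 0.7 the adjusted SE is 0.267 × √0.51 = 0.191, and 0.5/0.191 = 2.62, so power is Φ(0.66) = 75%. A difference in change has variance (2/n) × 2(1 − r).

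| Power, 28 per arm | r = 0.3 | r = 0.5 | r = 0.7 | r = 0.8 |
|---|---|---|---|---|
| 12-week level | 46% | 46% | 46% | 46% |
| Difference in change | 35% | 46% | 68% | 84% |
| Baseline-adjusted | 50% | 58% | 75% | 88% |

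At 35 per arm the level contrast has 55% power and the adjusted contrast 59%, 68%, 83% and 94%. The adjusted contrast is the best of the three at every r shown. A plain difference in change is worse than the level contrast when r is below 0.5.

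**The case against.** The strongest reply is that the plan already means to fit the same model to every variable. The sentence about group differences in all collected variables comes straight after the interaction sentence, contrasts of that kind usually follow a fitted model, and the Study Design section promises between-group effects on the associated outcomes. For outcomes measured only at baseline and end-of-study, the interaction in such a model is the between-arm difference in change. That reading is possible, but no sentence states it.

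A reader might infer more than the text supports:

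- *That the secondary outcomes get no comparison between arms, or only a comparison of raw values.* They do get group contrasts, which may be model-based. A 12-week contrast between randomized arms is unbiased, and chance baseline imbalance is already in its standard error. Adjustment adds precision; it does not rescue an invalid test.
- *That change is tested only by paired tests.* The per-group change contrasts name no outcome and may cover the secondary ones. The paired-test sentence is not confined to secondary outcomes either.
- *That the plan would credit a common drift to the intervention.* The drift cancels in the planned 12-week group contrast. The error arises only if paired results are presented as efficacy evidence, and the plan does not say they will be.
- *That the plan restricts the analysis to completers.* It does not say so. Complete pairs follow from the form of the test, the absence of a missing-data method and the deletion of surveys. The missing-data gap itself also affects the SPPB.

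All four qualifications stand. None of them supplies the missing statement.

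**Conclusion.** The point holds in a limited form. For the continuous secondary efficacy outcomes, the plan states neither a between-arm estimate of change nor a baseline-adjusted contrast. Its named test of change, with its non-normal fallback, is within-person and cannot carry a claim of treatment effect. The SPPB, which the protocol also lists as a strength measure, has the full model and is not affected. Acceptability, collected in the intervention arm only, and feasibility need no such estimate.

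The size is a 25% to 64% loss of available precision in the 12-week contrast at r = 0.5 to 0.8. For a 0.5 SD difference at 28 per arm, that is 46% power against 58% to 88%. At r = 0.3 the gain is small (46% to 50%). All of this rests on assumed correlations and an assumed effect. The 14 of 70 without a pair assumes that retention just meets its goal. For secondary outcomes of a pilot, this is a change that should be made because it costs almost nothing; it does not invalidate the trial.

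**What to change.** Add to the Aim 2 paragraph of V.2:

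1. Each continuous secondary efficacy outcome, listed by name, is analysed with PROC MIXED or ANCOVA on all available data. The reported effect is the 12-week between-arm difference adjusted for baseline, with its 95% CI. Extending the interaction model unchanged would give a difference in change, which is less precise, so the adjustment should be explicit.
2. For clearly non-normal outcomes, a between-arm rank-based or bootstrap version of the same contrast is used.
3. The paired t and signed-rank tests are descriptive within-arm summaries and are not evidence of efficacy.

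ANCOVA also needs the 12-week value. A mixed model that keeps baseline among the repeated responses can retain participants with a baseline only, but no model recovers surveys that have been deleted. The text should therefore say who contributes to each analysis and how that squares with the all-participants label.

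The cost is a few sentences and reuse of the planned SAS code across outcomes. There are no new data, visits or participants.
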